9.2.1 Study time frame

For the main analysis, the study population will comprise all adult OAC naïve (no OAC prescription in the previous 365 days, counted from the date of the first dispensation backward to the end of OAC supply) NVAF patients in Norway dispensed a prescription for an OAC (NOAC or warfarin) for the first time in the study period (cohort 1a), defined as from 1 January 2014 to 30 June 2018 (or later depending on availability of data) and followed until endpoint of interest, the end of the study period or death. Patients will be censored at a switch or a discontinuation.

For exploratory analysis, a second study population (cohort 1b) will comprise all adult NVAF patients in Norway that did not receive an OAC (NOAC or warfarin) in the study period, defined as above.

The look-back period will be at least 5 years from the possible earliest index date of NOACs (1 January 2014) going back to 1 January 2009 (available data cut). The minimum follow-up period will be 1 month and the estimated mean follow-up time will be 18 months.

[figure not shown]

Figure 1: Study design

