The duration of dispensation (DoD) will be set as the date of a dispensed prescription plus the estimated duration of that prescription (duration of OAC supply estimated from the dispensed pack-size and strength).

The following rules applies:

1. If the next dispensed prescription was for the same OAC within 30 days after end of DoD there was a continuous treatment
2. If a new dispensed prescription for another OAC occurred within DoD or within 30 days after end of DoD there was a switch in OACs (switching date = date of dispensation)
3. If the next dispensed prescription was for the same OAC more than 30 days after end DoD there was a discontinuation (discontinuation date = date of DoD + 30 days)

A 30-day gap period is included to take into account incomplete adherence to treatment. The figure underneath displays the three different scenarios. In sensitivity analyses the gap period will be varied from 30 days to 0 days, 15 days and 60 days, respectively.

[figure not shown]

Figure 4: Definition of continuation, switch and discontinuation

Patients to be included in the effectiveness and safety analysis should have a supply of OAC covering the event, plus a 30 days grace period for those patients discontinuing their therapy. Any event happening after the date of discontinuation plus 30 days or after a switch in OAC therapy will not be included.

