9.3.4 Outcome measures

9.3.4.1 Outcome definitions effectiveness

Cohort 1 and 2 (same for both cohorts):

The main efficacy endpoint is ischemic stroke defined by the following ICD10 codes:

I63x: Cerebral infarction

Overall stroke is defined by the following ICD10 codes:

I60x: Subarachnoid haemorrhage

I61x: Intracerebral haemorrhage

I62x: Other nontraumatic intracranial haemorrhage

I63x: Cerebral infarction

I64x: Stroke, not specified as haemorrhage or infarction

Events of systemic embolism will be analysed separately and in combination with ischemic and overall stroke. Systemic embolism is defined by the following ICD10 codes:

I74x: Arterial embolism and thrombosis

All-cause mortality will be analysed separately and in combination with ischemic and overall stroke plus systemic embolism.

Events of myocardial infarction will be analysed separately and is defined by the following ICD10 codes:

I21x: Acute myocardial infarction

I22x: Subsequent myocardial infarction

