9.4 Data sources

For cohort 1 three data sources will form the basis for the analyses, the Norwegian Census Register (FRG), the Norwegian Prescription Database (NorPD) and the Norwegian Patient Register (NPR). The FRG list all Norwegian residents from birth to death, including migration data and place of birth.

The NorPD is a register covering all prescriptions dispensed at pharmacies nationwide and data is available from 1 January 2004. Each medication is coded according to the Anatomical Therapeutic Chemical (ATC) system. The prescription registry also includes information about date of dispensation, quantity dispensed, the defined daily dose (DDD) of the dispensed drug and strength. NorPD does not cover drug administered during hospital stays, drugs used at nursing home or over-the-counter drugs. From March 2007 the NorPD includes the reimbursement code using either the ICD10 or the ICPC-2 coding systems.

The NPR was established in 2008 and contains all hospital visits (emergency visits, in-patient hospitalizations and outpatient ambulatory consultations), length of stay and procedures (surgical and medical) from all hospitals in Norway. Diagnoses are coded according to the International Classification of Diseases, 10th revision (ICD10). Medical and surgical procedures are coded based on the NOMESCO (The Nordic Medico-Statistical Committee) coding system. Both primary and all subsequent codes related to each admission will be retrieved. Lag time in NPR is approximately 4 months.

The registries are nation-wide and provision of the information is mandatory, which eliminates the risk of both selection and recall bias. The large and detailed dataset also makes it possible to adjust for risk factors and analyze in depth the different sources of bias and confounding. The registry holders will generate the datasets and release it in a coded and de-identified form, but with a unique identifier common to the three datasets making individual merging of the NorPD, NPR and FRG datasets possible.

Data from the registries will be linked using the unique 11-digit national identification number. NorPD is a pseudonymized register and the registry holder will according to national guidelines handle the linkage and release the dataset in a coded form so that all participants remain de-identified.

The following key variables will be retrieved from FRG;

- Age
- Gender (male, female)

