9.7 Data analysis

All data analyses will be performed using SAS statistical software version 9.4., and will be reported in a manner consistent with the Strengthening the Reporting of Observational Studies in Epidemiology (STROBE) guidelines.

Descriptive statistics will be used to present the data where continuous variables will be summarized as mean, standard deviation, median, minimum and maximum. Categorical variables will be described by frequencies and related percentages. Summaries will be reported separately for the elderly +75 years (cohort 1 and 2) and patients with renal impairment (cohort 2). Annual frequency of different OAC treatment during the study period in addition to adherence to each NOACs (high, moderate, low, and poor) will be presented. Also a separate analysis will be done to characterize patients with NVAf who have not been treated with OAC.

In the following, cohort 1 (registry) and cohort 2 (EMR) will be analyzed separately, but using the same analytical approaches.

The analyses will be performed on the total sample as well as on a confounder adjusted sample. It has to be kept in mind that analyses based on the overall sample (non-confounder adjusted sample) is prone to bias (see section 9.9).

Three separate propensity score models will be conducted and a 1:1 matching will be performed for:

- warfarin vs apixaban
- warfarin vs dabigatran
- warfarin vs rivaroxaban.

No matching to compare the NOACs among each other (e.g. apixaban vs rivaroxaban) will be performed due to underlying differences in prescribing preferences of different NOACs.

The propensity scores (PS) will be based on demographic variables and clinically relevant medical history, e.g. cardiovascular risk factors, comorbidities and concomitant medications at baseline.

Patients who switch or discontinue the OAC treatment will be censored at the date of switch or discontinuation. It cannot be ruled out that the switch of OAC (censoring) could be informative, but it is handled as uninformative censoring in the analyses.

Detailed methodology for propensity score modeling, matching, handling of missing data, summary and statistical analyses in this study will be documented in a Statistical Analysis Plan (SAP), which will be dated, filed and maintained by the sponsor. The SAP may modify the plans outlined in the protocol; any major modifications of primary endpoint definitions or their analyses would be reflected in a protocol amendment.

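### All-cause mortality and its composites are counted only on treatment, so censoring at discontinuation is likely to be informative for death, and Section 9.7.1 contradicts the follow-up rule

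*Protocol*

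**What the plan says.** Section 9.3.2 sets the counting rule for the whole effectiveness and safety analysis: "Patients to be included in the effectiveness and safety analysis should have a supply of OAC covering the event, plus a 30 days grace period" (the grace applies to patients who stop). It then adds: "Any event happening after the date of discontinuation plus 30 days or after a switch in OAC therapy will not be included". The discontinuation date in the same section already carries a grace period: "discontinuation date = date of DoD + 30 days". Section 9.2.1 says "Patients will be censored at a switch or a discontinuation", Section 9.2 lists discontinuation and switch among the censoring criteria, and Section 9.7 repeats "Patients who switch or discontinue the OAC treatment will be censored at the date of switch or discontinuation".

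Section 9.3.4.1 places death among the effectiveness outcomes and makes no exception for it: "All-cause mortality will be analysed separately and in combination with ischemic and overall stroke plus systemic embolism".

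On data coverage, Section 9.4 says "NorPD does not cover drug administered during hospital stays, drugs used at nursing home or over-the-counter drugs". On the censoring assumption, Section 9.7 says "It cannot be ruled out that the switch of OAC (censoring) could be informative, but it is handled as uninformative censoring in the analyses". That sentence covers switching; discontinuation is not mentioned there or in the limitations (Section 9.9).

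Section 9.7.1 gives a different rule for person-time: from first OAC use to the outcome, death or the end of follow-up, with no reference to discontinuation or switch.

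**The concern.** On-treatment counting is a recognisable choice for stroke and intracranial haemorrhage. It is harder to defend as the only analysis of death. A patient whose health is failing may stop collecting the drug before dying. A patient who enters a nursing home may stay anticoagulated but disappear from the prescription register. In both cases the patient is censored at a time related to the outcome, and a later death is not counted. How long after the last dispensing a death still counts depends on the days of supply assigned to that dispensing. These are fixed by tablets and dosing frequency for the NOACs and modelled for warfarin, so the loss need not be equal across drugs.

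At stake are a secondary outcome and the composites built on it, which a reader will use to judge net benefit. If Sections 9.3.2 and 9.7.1 are both followed literally, events are limited to treated time while person-time runs to the end of follow-up, and every rate is understated.

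**Working it through.** **1. The supply figures.** Section 9.3.2 assigns 100 tablets of rivaroxaban 100/1 = 100 days and 100 tablets of apixaban 100/2 = 50 days. Both reproduce. The packs are given as an example. Warfarin supply is imputed from a median daily amount by age and sex, and its length is not stated.

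**2. How long a death still counts after the last dispensing.** This is days of supply D plus grace G.
- G = 30 (censoring at the discontinuation date, Sections 9.2.1 and 9.7): 130 days for D = 100, 80 days for D = 50.
- G = 60 (30 days added to a discontinuation date that already includes 30, Section 9.3.2 read literally): 160 and 110 days.

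The planned gap sensitivity analyses (0, 15 and 60 days, with the gap applied once) give 100 v 50, 115 v 65 and 160 v 110 days. They move the window but keep the on-treatment restriction, and the 50-day difference stays. Rule 3 of Section 9.3.2 is worded for a patient who later collects the same drug. I applied the same date to a patient who never collects again.

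**3. Illustrative share of post-stop deaths that are dropped.** Assumptions, none of them from the protocol: the stop falls uniformly within the last supply, and survival after it is exponential with mean m days.

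Share dropped = exp(−G/m) × (m/D) × (1 − exp(−D/m))

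Example, D = 100, G = 30, m = 60: 0.607 × 0.600 × 0.811 = 0.295.

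| Mean survival m (days) | D=50, G=30 | D=100, G=30 | D=50, G=60 | D=100, G=60 |
|---|---|---|---|---|
| 60 | 41% | 30% | 25% | 18% |
| 120 | 64% | 53% | 50% | 41% |
| 180 | 74% | 65% | 63% | 55% |
| 365 | 86% | 81% | 79% | 74% |

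**4. Effect on all counted deaths.** If a share s of deaths follows such a stop and all others are counted, the counted fraction is 1 − s × (share dropped). Example, s = 0.25, m = 120, G = 30: 1 − 0.25 × 0.637 = 0.841 for D = 50 and 1 − 0.25 × 0.528 = 0.868 for D = 100, a ratio of 0.97. Over the whole table the loss is 4–22% of all deaths for s = 0.25 and 9–43% for s = 0.50. The ratio of counted deaths between the two supply lengths is 0.97–0.98 and 0.93–0.96 respectively.

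**5. What these figures are not.** They are not bias in a rate. Censoring removes the later person-time together with the later deaths, so a rate is biased only to the extent that mortality after stopping differs from mortality on treatment.

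**6. The rules side by side.** Sections 9.2, 9.2.1, 9.3.2 and 9.7 end follow-up at discontinuation or switch; Section 9.7.1 does not. They cannot all hold for the same incidence rate.

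**The case against.** The best defence is that on-treatment analysis is a declared design choice, that Section 9.7 admits switching may be informative, and that Section 9.7.2 leaves further sensitivity analyses to the SAP, which is not at hand. Much of this stands. Replacing the on-treatment analysis would change the question being asked, so nothing more than an added analysis is warranted. A missing all-follow-up sensitivity analysis for stroke and intracranial haemorrhage is no finding, because the SAP may contain one. What does not go away is that the protocol's own rule excludes these deaths, and its acknowledgement omits discontinuation.

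A reader might infer more: that the 50- against 100-day contrast shows a spurious mortality ratio of about 0.72–0.83, and hence one against warfarin. The protocol does not support that.
- The contrast is apixaban against rivaroxaban, and Sections 9.7 and 9.9 rule out comparisons between NOACs.
- It covers only deaths after a terminal stop, and assumes G = 30; with G = 60 it is about 0.80–0.91.
- It takes an example pack as the actual dispensing pattern, although Section 9.3.2 also counts the number of packages.
- It ignores the person-time removed.

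How often stopping precedes death is likewise not stated in the protocol; it is a plausible premise, not a documented one.

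**Conclusion.** The concern holds as a secondary-outcome point that should be corrected. The written rule counts all-cause mortality and its composites only on treatment, the dispensing data misread institutional supply as discontinuation, and the resulting censoring is likely to be informative for death. The planned gap variations cannot reveal this. Under the stated survival assumptions about 30–86% of post-stop deaths (30 days of grace) or 18–79% (60 days) would fall outside the window. The difference between supply lengths in all counted deaths is much smaller than the difference in post-stop deaths alone. Direction and size against warfarin cannot be derived, because warfarin supply, actual dispensing lengths, the share of deaths after stopping and survival after stopping are not given. The conflict between Section 9.7.1 and the other sections, and the doubt over one or two 30-day periods, follow from the text and need no assumption.

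**What to change.** - In Sections 9.3.2, 9.7 and 9.7.1, state one end-of-follow-up rule for the on-treatment analysis, so that events and person-time stop on the same date.
- In Section 9.3.2, say whether the 30 days apply once or twice, and give the discontinuation date for a patient with no further dispensing.
- For all-cause mortality and the composites containing it, add an analysis by index OAC from the index date to death, emigration or the end of the study. Use census-register dates, and NPR events for the composites. Report it beside the on-treatment analysis.
- In Section 9.7 or 9.9, extend the statement on informative censoring to discontinuation, and name the nursing-home and in-hospital gap as one cause.

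The cost is protocol wording and one extra analysis run; no new data are needed. The drawback is that the by-index-drug estimate is diluted by switching and stopping, which is why both should be shown.

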9.3.3 Estimation of OAC adherence

Proportion of days covered (PDC) will be estimated for each individual from the index medication date and onwards. The PDC is defined as the number of days that the index medication was on hand during the time period divided by the total number of days in the period. For instance if the length of the time period is 100 days and the NOAC supply covers 50 days, the adherence is estimated to 50%.

Likewise, the age- and sex-specific median doses of warfarin (using the two methods described in 9.3.2) will be used to calculate to warfarin supply.

If the OAC supply last longer than the study period the adherence is set to 100%. The proportion of days covered (PDC) will take into account the patient's entire follow-up period, defining end of study period as death, end of study, migration, discontinuation or switch of OAC therapy. In addition to the entire period, adherence will also be estimated at fixed time intervals after OAC index date, i.e. 3 months (90 days), 6 months (180 days), and 9 months (270 days), 1 year (365 days), 2 years (730 days) and 3 years (1095 days).

Consecutive dispensations of the same OAC will be combined and corrected for overlap. For treatment gaps equal or less than 30 days of the previous OAC dispensation it is assumed the patient is on continuous therapy. The length of the gap period will be varied in sensitivity analyses down to 0 and 15 days and up to 60 days.

Some patients switch to another NOAC during follow-up and the day of switch will be defined as the end of the time period. Separately, the PDC for use of any OAC during the study period will be estimated, which accounts for therapy switching during follow-up.

PDC will be estimated as the mean PDC for each OAC as well as grouped into four categories of high adherence (≥ 0.80), moderate adherence (0.50-0.79), low adherence (0.20-0.49) and poor adherence (<0.20). Adherence will also be reported as dichotomized using the conventional PDC of <0.80 or ≥ 0.80 as cutoff. Percentage point differences between OAC user groups will be presented. Analyses of OAC adherence will account for differences in follow-up time and baseline characteristics, such as standard and reduced dosing level.

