9.2 Setting

The study will be undertaken in Norway and will comprise all adult patients with NVAF who initiated treatment with either a NOAC or warfarin during the study period for the first time (OAC naïve first-time users). Study endpoints, discontinuation, switch to another OAC, death or end of study period will serve as censoring criteria.

The NVAF study population is defined in accordance with the 2018 European Heart Rhythm Association practical guide on the use of non-vitamin K antagonist oral anticoagulants in patients with atrial fibrillation, which define NOAC eligibility in NVAF patients as atrial fibrillation in the absence of rheumatic mitral stenosis or a mechanical heart valve.

Cohort 1 (registry study): Registries in Norway are nation-wide and provision of the information is mandatory, which eliminates the risk of both selection and re-call bias. The large and detailed dataset also makes it possible to adjust for other risk factors on which information is available.

In cohort 2, patients with NVAF diagnosis will be identified through extraction of patient-level data from EMRs from a number of hospitals in Norway, in order to describe these patients more closely regarding their clinical characteristics that are not available in nation-wide registers (e.g., in-patient treatments, anthropometric data and laboratory test results). This part of the

¹ Source: <http://www.legemiddelverket.no>

study is a pilot that will test the operational feasibility of accessing and linking the regional EMR data to the Norwegian Health Registers. Should the access to the regional EMR be granted, patients in cohort 2 will be identified and their EMRs extracted using the Pygargus Customized Extraction Platform (CXP). The extraction program has been used in a number of research projects since 2005 in the Swedish and Norwegian health care systems (6, 7). De-identified individual level data on age, gender, prescriptions, diagnoses, measures, laboratory tests, health care professional (HCP) visits, referrals, etc. can be collected from the EMRs into an encrypted database.

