9.3.2 OAC exposure

New OAC exposure is defined as a single or series of dispensation of an OAC starting in the period from 1 January 2014 to end of study period. The duration of the observation period together with the pack size of each prescription will be used to calculate the length of a patient's OAC exposure. To ensure a minimum of one month follow-up data for all subjects on OAC treatment, inclusion (cut-off index OAC date) will be stopped one month before the end of available follow-up data.

For each dispensation, the OAC days of supply will be computed using information on date of dispensation, the number of packages and the pack-size dispensed. Since NOACs are prescribed in a fixed dose, the number of days of supply strictly corresponds to amount dispensed accounting for a recommended frequency of daily dosing. The NorPD contains information on tablet strength, pack-size and number of packages dispensed, and we assumed, according to the labelling, twice daily dosing for apixaban and dabigatran and once daily dosing for rivaroxaban, e.g. a patient supplied one package of a 100 tablet package of rivaroxaban will have a supply lasting for 100 days, whereas a 100 tablet package of apixaban will provide a supply lasting 50 days.

Computing the warfarin supply is not straightforward as we lack information on both dosing instructions and International Normalised Reference values (INR) in the registries.

Two different methods will be applied to compute the warfarin exposure;

1. EMR data (from cohort 2) holds information on both INR and dosing. Median mg/day of warfarin will be computed in relation to age (in 5-year categories) and gender (females and males). The median mg/day will be used as a basis for computing the warfarin supply in cohort 1.
2. Registry data (from cohort 1) using the length of each time interval in days between dispensation and corresponding dispensed warfarin amount for the time interval will be used to compute the median daily warfarin use for each patient. The calculated median mg/day for all patients using warfarin in the study period, in relation to age group and gender as with method 1, will subsequently be used in the computation of warfarin supply for each dispensation.

Similarly, the same methods will be used to set the end of OAC supply date during the pre-index period to be able to determine if a patient was OAC naïve or not (≥ 365 days without OAC supply prior to index date).

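### Method 2 builds the average level of warfarin non-adherence into the assumed daily dose, so warfarin PDC under that method cannot be compared with NOAC PDC

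*Protocol*

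**What the plan says.** Protocol section 9.3.2 gives two ways to set the daily warfarin dose.

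- Method 1 uses the electronic records: "EMR data (from cohort 2) holds information on both INR and dosing". Section 9.2 makes this source conditional: "Should the access to the regional EMR be granted".
- Method 2 uses the registry, "using the length of each time interval in days between dispensation and corresponding dispensed warfarin amount for the time interval", to obtain a median daily use for each patient. The dose applied to every dispensation is then a group figure: "The calculated median mg/day for all patients using warfarin in the study period, in relation to age group and gender as with method 1".

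For NOACs the same section states that "the number of days of supply strictly corresponds to amount dispensed accounting for a recommended frequency of daily dosing".

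Section 9.3.3 sets the adherence measure, with the length of the period as its denominator: "The PDC is defined as the number of days that the index medication was on hand during the time period divided by the total number". For warfarin, "the age- and sex-specific median doses of warfarin (using the two methods described in 9.3.2) will be used to calculate to warfarin supply". Neither method is named as the main one. The section then plans mean PDC for each OAC, four adherence categories and a 0.80 cut-off, and adds: "Percentage point differences between OAC user groups will be presented".

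**The concern.** Amount dispensed divided by time to the next dispensation is what patients got through, missed tablets included. It is not the dose they were told to take. Using it to convert packs into days of supply means that warfarin refilling is judged against warfarin refilling. NOAC refilling is judged against an external standard, the label.

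The two PDC figures then measure different things, yet the plan subtracts one from the other. A reported warfarin-NOAC adherence gap, or a difference in the share above 0.80, could come wholly from the choice of denominator. Section 9.9 says that real intake is unknown. That applies to every OAC and does not tell the reader that the denominators differ in kind.

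**Working it through.** **The plan's own figures.** 50 days of supply in 100 days gives 50/100 = 50%. A pack of 100 rivaroxaban tablets at one a day lasts 100 days, and 100 apixaban tablets at two a day last 50 days. All agree with sections 9.3.2 and 9.3.3.

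**Algebra.** Let patient i need D_i mg/day, take a share A_i of it, and receive packs of P mg. The refill interval is P/(D_i·A_i). Let M1 = median(D) be the method 1 dose and M2 = median(D·A) the method 2 dose, within an age-sex stratum. Ignoring end effects, and counting gap days as uncovered:

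- NOAC PDC = A_i
- warfarin PDC, method 1 = min(1, D_i·A_i / M1)
- warfarin PDC, method 2 = min(1, D_i·A_i / M2)

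If everyone takes the same share a, then M2 = a·median(D), and method 2 gives min(1, D_i/median(D)). The share a has dropped out. This needs no assumption about dose spread.

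**One-pack illustration (80% intake, no dose spread).** A 100-day pack is refilled at 100/0.80 = day 125. NOAC PDC = 100/125 = 0.80. Method 2 sets the warfarin supply at 125 days, so PDC = 125/125 = 1.00, a difference of 20 points.

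**The difference does not simply equal the share missed.** At 70% intake the refill falls at 100/0.70 = day 143, a gap of 43 days. That exceeds the 30-day rule, so the period ends at day 130. NOAC PDC = 100/130 = 0.77, and the difference is about 23 points, not 30.

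**Simulation.** There were 4,000 patients per scenario, with follow-up of 548 days (the 18-month mean in section 9.2.1). Assumptions not in the protocol: 250 mg packs, median dose 5 mg/day (so 50 days per pack), dose CV 0 to 0.5, and mean intake 60% to 100% with SD 0 to 0.15. The figures below use no truncation at 30-day gaps. Ranges run over the intake SDs tried.

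| Mean intake | NOAC | Method 2, CV 0, SD 0 | Method 2, CV 0.4 | Method 1, CV 0.4 |
|---|---|---|---|---|
| 60% | 0.62–0.64 | 1.00 | 0.87–0.89 | 0.64 |
| 70% | 0.72–0.73 | 1.00 | 0.87–0.88 | 0.71–0.72 |
| 80% | 0.81–0.82 | 1.00 | 0.88–0.89 | 0.78–0.79 |
| 90% | 0.91 | 1.00 | 0.88 | 0.84 |
| 100% | 1.00 | 1.00 | 0.88 | 0.88 |

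NOAC values can sit slightly above true intake because follow-up ends while a pack is in use. At 80%, eight intervals of 62.5 days make 500 days, and the last 48 days are covered: (400 + 48)/548 = 0.82.

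With CV 0.4, method 2 barely moves as intake goes from 60% to 100%. It exceeds the NOAC value at 60% to 80% and falls below it from 90%. With CV 0.2 it still exceeds the NOAC value at 90% (0.92–0.93 against 0.91) and falls below it at 95% (0.93 against 0.95). The reversal occurs because PDC is capped at 1: patients who need less than the median dose show false gaps, and those who need more cannot offset them. Truncating at gaps over 30 days did not change these directions.

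**The 0.80 cut-off (CV 0.4).** At 70% intake (SD 0.15), 69% of warfarin users under method 2 reach it against 33% of NOAC users. At 90% (SD 0.10), it is 72% against 88%.

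**What survives between patients.** The correlation of true intake with method 2 PDC is 0.89–0.98 without dose spread. At CV 0.4 it is about 0.5 for mean intake of 60–80% and 0.15–0.33 for 90–95%.

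**The case against.** Five points can be made for the plan.

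- A reader might infer that warfarin non-adherence becomes invisible. It does not. Section 9.3.2 applies an age-sex median rather than the patient's own rate, so slower-than-median refilling still lowers PDC, as the correlations show. What is lost is the average level. This stands.
- A reader might also infer a bias always against the NOACs. The document does not support that, and the table shows the sign changing with dose spread and true intake. This stands, but an unknown sign makes the contrast no more interpretable.
- Section 9.3.3 treats gaps of up to 30 days as continuous therapy. If that means gap days count as covered, the 25-day gap in the illustration disappears and NOAC PDC is also 1.00. The text can be read either way. The 50% worked example points towards uncovered days counting as uncovered, but it does not settle the matter. The illustration therefore carries that condition; the cancellation in the dose does not.
- Method 1 is not circular and is also planned. That helps, but it depends on EMR access and is not given precedence. If access is refused, method 2 is the only warfarin PDC.
- The stakes are limited. Section 8.3 lists adherence as exploratory and names NOACs, and section 9.7 presents the adherence categories for NOACs. Warfarin enters the contrast only through the general wording of section 9.3.3. This stands and lowers the priority.

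Leaving the matter to the SAP is not a full answer, because sections 9.3.2 and 9.3.3 already fix both the method and the comparison.

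**Conclusion.** The point holds in this form: under method 2 the average level of warfarin adherence cannot be identified, and warfarin-NOAC differences in PDC, in adherence categories and in the share above 0.80 are not comparable. The cancellation is algebraic. The sizes are not: 20 points in the 80% illustration requires no dose spread and gap days counted as uncovered, and the simulated values rest on assumed dose spread and intake. The bias favours warfarin when intake is below 100% and doses do not vary, and it can reverse when doses vary widely and intake is high.

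Method 1 removes the circularity but is not free of error when one median dose stands in for individual doses. At 90% intake and CV 0.4 it gives 0.84 against a NOAC value of 0.91. Method 2 happens to lie closer there (0.88), but only because it gives about 0.88 at any intake. The NOAC adherence objective in section 8.3 is untouched. This is a change worth making, of modest priority.

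**What to change.** In section 9.3.3:

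- Base warfarin PDC used in any comparison with NOACs on method 1 only: the patient's own recorded EMR dose in cohort 2, and the age-sex median EMR dose in cohort 1. Table 5 already lists OAC dosing for modelling warfarin exposure in the registry cohort.
- Report method 2 warfarin PDC, if at all, descriptively, with the circularity stated and no percentage-point difference against NOACs.
- If EMR access is refused, limit between-group PDC differences to the three NOACs.
- State whether days in a gap of 30 days or less count as covered.

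Do not offer time to discontinuation under method 2 as an independent substitute. Section 9.3.2 builds the discontinuation date from the same estimated supply.

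The cost is a few sentences and fewer tables. There would be no warfarin-NOAC PDC contrast without EMR access, and the cohort 1 contrast under method 1 would still carry the error of a single median dose, which should be stated beside the result.
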